3.7.1.2 Baseline (Day 1)

If the subject continues to be eligible for the trial after the screening period, the following procedures will be performed:

- An assessment of all inclusion and exclusion criteria will be made to confirm the subject's eligibility for the trial.
- A qualified and certified rater will administer the YMRS, CGI-BP, CCI [REDACTED]
[REDACTED]
- The investigator (or qualified designee) who is adequately trained will complete the "Baseline/Screening" C-SSRS form.
- Vital sign measurements (body temperature, blood pressure, and heart rate) will be recorded. Blood pressure and heart rate are to be measured in the following order: supine and standing after the subject has been in each position at least 3 minutes. See Table 3.4.3-1 for exclusions based on outcome of screening vital sign measurements.
- A standard 12-lead ECG will be performed after the subject has been supine and at rest for at least 5 minutes. See Table 3.4.3-1 for exclusions based on ECG results.
- Adverse events and concomitant medications will be recorded.

3.7.1.3 Randomization

Once subject eligibility has been confirmed at baseline, the following will be performed on Day 1:

- Trial personnel will access the IWRS or equivalent to register the visit and to obtain blister card assignment(s) for double-blind IMP. The assigned IMP will be dispensed to the subject.

3.7.1.4 Treatment Phase - Day 4

The following procedures will be performed on Day 4 (\pm 1 day):

- A qualified and certified rater will administer the YMRS and CGI-BP.
- The investigator (or qualified designee) who is adequately trained will complete the "Since Last Visit" C-SSRS form.
- CCI [REDACTED]
- Vital sign measurements (body temperature, blood pressure, and heart rate) will be recorded. Blood pressure and heart rate are to be measured in the following order: supine and standing after the subject has been in each position at least 3 minutes.
- A urine pregnancy test will be performed for all WOCBP. All positive results must be confirmed by a serum pregnancy test. Subjects with a positive serum pregnancy test result will be withdrawn from the trial.
- Adverse events and concomitant medications will be recorded.
- IMP will be dispensed to the subject (Days 4, 5, and 6).
- Drug accountability will be performed.

3.7.1.5 Treatment Phase - Day 7

The following procedures will be performed on Day 7 (\pm 1 day):

- A qualified and certified rater will administer the YMRS and CGI-BP.
- The investigator (or qualified designee) who is adequately trained will complete the "Since Last Visit" C-SSRS form.
- CCI [REDACTED]
- Vital sign measurements (body temperature, blood pressure, and heart rate) will be recorded. Blood pressure and heart rate are to be measured in the following order: supine and standing after the subject has been in each position at least 3 minutes.
- Adverse events and concomitant medications will be recorded.

- IMP will be dispensed to the subject (Days 7 through 13).
- Drug accountability will be performed.

3.7.1.6 Treatment Phase - Day 14

The following procedures will be performed on Day 14 (\pm 1 day):

- A qualified and certified rater will administer the YMRS, CGI-BP, CCI [REDACTED]
- The investigator (or qualified designee) who is adequately trained will complete the "Since Last Visit" C-SSRS form.
- CCI [REDACTED]
- Vital sign measurements (body temperature, blood pressure, and heart rate) will be recorded. Blood pressure and heart rate are to be measured in the following order: supine and standing after the subject has been in each position at least 3 minutes.
- Adverse events and concomitant medications will be recorded.
- IMP will be dispensed to the subject (Days 14 through 21).
- Drug accountability will be performed.
- Subjects who, in the opinion of the investigator, have clinically improved from their baseline assessments with mild to no manic symptoms, and are stable enough to be treated on an outpatient basis, including no risk of suicide assessed by the C-SSRS, may be discharged and will continue as outpatients for the last week of double-blind treatment.
- Those subjects who are discharged early will be administered IMP for the last week of treatment that is clearly labeled with the trial number, subject ID, and subject initials. Subjects will be counseled on the importance of taking the IMP.

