	
C
      
Safety Endpoints:
 
Standard safety variables will include AEs, clinically significant changes in: ECGs, vital signs, clinical laboratory tests, use of concomitant medications, changes in body weight, and PE.
 
CCI
  
Suicidality will be assessed using the C-SSRS.

Statistical Methods:
	
For analysis of the double-blind treatment phase data, baseline is defined as the last available measurement prior to the first dose of double-blind IMP. The primary analysis will be performed on the Efficacy Sample which includes all

randomized subjects who took at least 1 dose of IMP in the double-blind treatment phase and who have both a baseline value and at least 1 post-randomization YMRS Total Score during the double blind treatment phase. CCI

[REDACTED]

[REDACTED]

[REDACTED]

The primary efficacy endpoint is the change from baseline to Day 21 in the double-blind treatment phase in the YMRS Total Score. The trial will compare the placebo arm to the brexpiprazole arm, randomized at a ratio of 1:1, with an overall significance level of 0.05 for the primary endpoint.

CCI [REDACTED]

The planned sample size of 304 evaluable subjects (152 in each treatment arm) will yield at least 90% power to detect the treatment effects at a 2-tailed significance level of 0.05.

A sufficient number of subjects will be enrolled and randomized to achieve approximately 304 evaluable subjects in the double-blind treatment phase CCI

[REDACTED]

the total number of subjects to be randomized is 320 (160 in each treatment arm).

	
In order to ensure 304 evaluable subjects, ^{CCI} [REDACTED]

Trial Duration:
	
The duration of this trial for an individual subject who completes the trial without early withdrawal is approximately 8 weeks. This is inclusive of a maximum 14-day screening period, a 3-week double-blind treatment period, and a safety follow-up via telephone contact or clinic visit 21 (\pm 2) days after the last dose of IMP. Subjects who complete all trial visits through the Day 21 visit may be offered entry into an optional open-label rollover trial.

Table of Contents

Protocol Synopsis	2
Table of Contents	7
List of In-text Tables	12
List of In-text Figures	13
List of Appendices	14
List of Abbreviations and Definitions of Terms	15
1 Introduction	17
1.1 Nonclinical Data	17
1.2 Clinical Data	18
1.3 Known and Potential Risks and Benefits	18
2 Trial Rationale and Objectives	19

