3.1 Type/Design of Trial

This will be a 3-week, multicenter, randomized, double-blind, placebo-controlled trial of brexpiprazole in subjects diagnosed with bipolar I disorder (current manic episode with or without mixed features) according to the *Diagnostic and Statistical Manual of Mental Disorders, Fifth Edition* (DSM-5; updated terminology replaces “mixed episodes” with the descriptor of “mixed features”). The total duration of the trial is up to 8 weeks, including screening, double-blind treatment, and follow-up. See Figure 3.1-1 for a schematic of the trial design.

The trial will be organized as follows:

Screening Phase: The screening period will begin after written informed consent has been obtained and will take place between Day -14 and Day -1 prior to randomization. Hospitalization will begin with the signing of the informed consent form (ICF) for subjects who are not already hospitalized at the time of the initial screening visit. The purpose of the screening period is to assess eligibility criteria and to washout prohibited concomitant medication. Subjects will be between 18 and 65 years of age, inclusive, at the time of screening, will have a diagnosis of bipolar I disorder, and will be experiencing a manic episode with or without mixed features as defined by the DSM-5 criteria. An interactive web response system (IWRS) or equivalent will be used to obtain an

identification (ID) number for each subject with documented consent. Although the screening period will continue up to administration of the first dose of investigational medicinal product (IMP), screening procedures should be initiated with a sufficient amount of time allotted in order to obtain laboratory results and electrocardiogram (ECG) results from the central reader prior to randomization. The sponsor reserves the right to utilize external quality oversight methods to ensure the validity of diagnosis, severity of illness, and other factors determining appropriateness of subject selection.

[figure not shown]
All subjects must agree to discontinue all prohibited medications during the screening period in order to meet the protocol-specified washout periods.

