3.4.3 Exclusion Criteria

Subjects will be excluded if they meet any of the exclusion criteria in Table 3.4.3-1.

Table 3.4.3-1 Exclusion Criteria	
	Sex and Reproductive Status
1.	Sexually active males or WOCBP who do not agree to practice 2 different methods of birth control or remain abstinent during the trial and for 30 days after the last dose of IMP. If employing birth control, 2 of the following precautions must be used: vasectomy, tubal ligation, vaginal diaphragm, intrauterine device, birth control pill, birth control implant, birth control depot injection, condom with spermicide, or sponge with spermicide.
2.	Females who are breastfeeding and/or who have a positive pregnancy test result prior to receiving IMP.
	Target Disease
3.	Subjects with a history of DSM-5 diagnosis other than bipolar I disorder, including schizophrenia, schizoaffective disorder, major depressive disorder, attention-deficit/hyperactivity disorder, delirium, dementia, amnesic, or other cognitive disorders. Also, subjects with borderline, paranoid, histrionic, schizotypal, schizoid, or antisocial personality disorder. All other current diagnoses must be discussed with the medical monitor.
4.	Subjects whose current manic episode has lasted for more than 4 weeks overall, or who have required hospitalization > 21 days for the current acute episode at the time of the screening visit, excluding hospitalization for psychosocial reasons.
5.	Subjects who have had initiation of, or a change in, psychotherapy for the treatment of bipolar disorder symptoms within 28 days prior to the screening visit or if it is anticipated that the subject will have a change in psychotherapy during the trial.
6.	Subjects with manic symptoms that are better accounted for by another general medical condition or direct physiological effects of a substance (eg, medications).
7.	Subjects considered unresponsive to clozapine or who are only responsive to clozapine.
8.	Subjects with bipolar I disorder who are considered resistant or refractory to treatment for manic symptoms by history.
9.	Subjects who have had electroconvulsive treatment within the past 2 months.
10.	Use of psychotropic medications (other than benzodiazepines) within 7 days of the baseline YMRS.
11.	Rapid cyclers with more than 6 episodes in the previous year.

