^aScreening begins when the ICF is signed and will take place between Day -14 and Day -1; however, screening procedures should be initiated with a sufficient amount of time allotted in order to obtain laboratory results and ECG results from the central reader prior to randomization. Review of inclusion/exclusion criteria at baseline will be based on assessments performed during screening. Hospitalization will begin with the signing of the ICF for subjects who are not already hospitalized at the initial screening visit. Note: In the rare circumstance when a subject must leave the inpatient facility temporarily (eg, family emergency or doctor visit), a temporary day pass may be granted. For such a request, sites must first contact the medical monitor for explicit authorization and guidance on procedures. A medical monitor approved day pass is good for the day requested only, and subjects must return to the site the same day (eg, in the evening).

^bIf a subject discontinues prematurely before Day 21, procedures noted for Day 21 must be completed at the ET visit.

^cConsists of telephone contact or clinic visit (investigator's discretion) for evaluation of safety 21 days after the last dose of IMP and applies only to subjects who do not enter the optional open-label rollover trial.

^dInformed consent must be obtained prior to any trial-related procedures. CCI

^eAll medications taken within 30 days of screening will be recorded. In addition, all prescription and non-prescription medications taken during the trial will be recorded as concomitant medications.

^fTo be eligible for the trial, subjects must have a YMRS score ≥ 24 at screening and baseline.

^gCCI

^hTo include measurement of height at screening only and waist circumference at screening and Day 21.

ⁱVital signs include body weight, body temperature, systolic blood pressure (SBP), diastolic blood pressure (DBP), and heart rate. Blood pressure and heart rate will be measured in the following order: supine and standing after the subject has been in each position for at least 3 minutes. Vital signs scheduled for the same visit as blood samples are to be completed before blood is drawn.

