3.7.1 Schedule of Assessments

3.7.1.1 Screening (Day -14 to -1)

The screening period begins after consent has been obtained. Consent should also be obtained for optional FBR for those subjects that want to participate. Although the screening period takes place between Day -14 and Day -1, subjects will participate in screening activities for a minimum of 1 day. After a subject has provided consent, sites will obtain a subject ID number for the subject by accessing the IWRS or equivalent. Screening evaluations will include the following:

- Hospitalization will begin once the subject signs the ICF for subjects who are not already hospitalized at the time of the screening visit.
- A qualified and certified rater will administer the YMRS CCI.
- An assessment of all inclusion and exclusion criteria will be made to determine the subject's eligibility for the trial.
- Demographic data will be recorded.
- A general clinical evaluation will be performed, including concurrent medical conditions, medical history over the past 2 years, and medical history beyond 2 years which is considered to be clinically relevant per the investigator's judgment.
- Psychiatric history will be recorded, including the DSM-5 diagnosis of bipolar I disorder that will be made by an adequately trained and experienced clinician and will be confirmed by the administration of the MINI.
- Medications (including those that were taken within 30 days of screening) will be recorded. In addition, all prescription and non-prescription medications taken during the trial will be recorded as concomitant medications. Details of prohibited/restricted medications are provided in Table 4.1-1 and Table 4.1-2.
- Washout from prohibited concomitant medications, if applicable (Table 4.1-1).
- CCI
- The investigator (or qualified designee) who is adequately trained will complete the "Baseline/Screening" C-SSRS form to exclude subjects with a significant risk of suicidal behavior (see Table 3.4.3-1).
- A complete physical examination (including height and waist circumference) will be performed.
- Vital sign measurements (body weight, body temperature, blood pressure, and heart rate) will be recorded. Blood pressure and heart rate are to be measured in the following order: supine and standing after the subject has been in each position at least 3 minutes. See Table 3.4.3-1 for exclusions based on outcome of screening vital sign measurements.

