- A standard 12-lead ECG will be performed after the subject has been supine and at rest for at least 5 minutes. See Table 3.4.3-1 for exclusions based on ECG results.

- Blood samples for clinical laboratory tests (hematology, coagulation parameters, and serum chemistry, including prolactin, HbA1c, and thyroid-stimulating hormone [TSH] with reflex to free thyroxine [T₄] if the result for TSH is abnormal, and lithium, valproate, and carbamazepine levels) should be drawn after a minimum 8-hour fast at screening. See Table 3.4.3-1 for exclusions based on outcome of screening clinical laboratory tests. Note: if lithium, valproate, or carbamazepine levels are outside of the listed exclusionary range, they may be reassessed prior to randomization.
- Samples will be obtained for blood alcohol testing. See Section 3.4.3 for details regarding subjects with a positive blood alcohol test.
- CCI [REDACTED]
- Urine will be collected from all potential subjects for urinalysis and urine screen(s) for drugs of abuse. See Section 3.4.3 for exclusions based on outcome of screening urinalysis and urine screen(s) for drugs of abuse.
- A urine pregnancy test will be performed for all women of childbearing potential (WOCBP). All positive results must be confirmed by a serum pregnancy test. Subjects with a positive serum pregnancy test result will be excluded from the trial.
- Adverse events will be recorded beginning with the completion of the consent process.
- Trial personnel will access the IWRS or equivalent to register the visit (initial visit only).

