ALP = alkaline phosphatase; BUN = blood urea nitrogen; GGT = gamma glutamyl transferase; LDH = lactic dehydrogenase; MCHC = mean corpuscular hemoglobin concentration; RBC = red blood cell; WBC = white blood cell.

Any value outside the normal range will be flagged for the attention of the investigator who must indicate whether or not a flagged value is of clinical significance. If one or more values are questionable, the test(s) may be repeated. If the result of any test (or repeat test, if done) is indicated as clinically significant in the samples taken during the screening period, the subject will NOT be enrolled into the trial without the permission of the medical monitor. In addition, follow-up unscheduled laboratory tests should be performed if clinically significant abnormalities are observed. Unscheduled laboratory tests may be repeated at any time at the discretion of the investigator for appropriate medical care. Refer to Appendix 3 for criteria for identifying values of potential clinical relevance.

The following laboratory test results at screening are exclusionary:

- Platelets $\leq 75000/\text{mm}^3$
- Hemoglobin $\leq 9 \text{ g/dL}$
- Neutrophils, absolute $\leq 1000/\text{mm}^3$
- Aspartate aminotransferase (AST) $> 2 \times$ upper limit of normal (ULN)
- Alanine aminotransferase (ALT) $> 2 \times$ ULN
- Creatine phosphokinase (CPK) $> 3 \times$ ULN, unless discussed with and approved by the medical monitor
- Creatinine $\geq 2 \text{ mg/dL}$

The total volume of blood to be collected during the trial per subject is expected to be approximately 50 mL.

A pregnancy test will be conducted in WOCBP prior to trial intervention; results must be available prior to the administration of the IMP. Pregnancy tests can be performed at any point during the trial if pregnancy is suspected.

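### The only scheduled pregnancy test before dosing can be up to 14 days old at the first dose, and the next one, on Day 4, comes too late to inform Exclusion 2

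*Protocol*

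**What the plan says.** Exclusion 2 (Protocol Table 3.4.3-1) keeps out "Females who are breastfeeding and/or who have a positive pregnancy test result prior to receiving IMP". Section 3.7.3.2 adds: "A pregnancy test will be conducted in WOCBP prior to trial intervention; results must be available prior to the administration of the IMP". It sets no maximum age for that result.

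The pregnancy row of Table 3.7-1 is marked at screening, Day 4 and Day 21/ET, and the baseline cell is empty. The visit lists agree. A urine test with serum confirmation of positives appears in Sections 3.7.1.1, 3.7.1.4 ("A urine pregnancy test will be performed for all WOCBP") and 3.7.1.7. None appears in Section 3.7.1.2 (baseline) or 3.7.1.3 (randomization).

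Screening "will take place between Day -14 and Day -1 prior to randomization" (Section 3.1). Footnote a of Table 3.7-1 states: "Review of inclusion/exclusion criteria at baseline will be based on assessments performed during screening". Dosing begins on Day 1 (Section 3.2). Under Section 3.7.1.4, a positive serum result at Day 4 leads to withdrawal.

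The type of test is described in three ways: serum in the synopsis, urine with serum confirmation in Section 3.7.1.1, and either or both in Section 5.5.

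**The concern.** Exclusion 2 is a condition on the woman's status before her first dose, yet the plan's second look comes just after that dose. A Day 4 result cannot change whether she is randomized or dosed; if confirmed positive, it can only end her participation. Other entry conditions are looked at again on Day 1: Section 3.7.1.2 repeats the YMRS, C-SSRS, vital signs and ECG.

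The stake is subject safety and how well one eligibility criterion is verified. Each such case would mean fetal exposure if the woman is on active drug, an immediately reportable event (Section 5.1), withdrawal of a randomized and dosed subject, and follow-up of the infant for at least 6 months (Section 5.5).

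**Working it through.** **Step 1: the plan's own duration figure.** The synopsis gives about 8 weeks per subject and says "This is inclusive of a maximum 14-day screening period, a 3-week double-blind treatment period", plus follow-up 21 days after the last dose. 14 + 21 + 21 = 56 days = 8.0 weeks. The figure reproduces, so the 14-day maximum is the intended one.

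**Step 2: age of the screening test at the first dose.** The first dose is on Day 1. Assume there is no Day 0, so Day -1 is the day before Day 1.
- Tested on Day -14: 14 days old.
- Tested on Day -1: 1 day old. This is allowed, since "subjects will participate in screening activities for a minimum of 1 day" (Section 3.7.1.1).

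Counting a Day 0 would make these 15 and 2 days.

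**Step 3: doses taken before the second test.** Day 4 ± 1 is Day 3 to 5. If the test precedes that day's dose, doses already taken = test day − 1, so 2, 3 or 4. If it follows the dose, 3, 4 or 5. The longest gap between the first two scheduled tests (Day -14 to Day 5, no Day 0) is 18 days.

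**Step 4: does another provision close the gap?**
- Section 3.7.3.2: met by a Day -14 result, because no maximum age is given.
- Footnote a: lets the baseline eligibility review rest on screening.
- Footnote m and Section 5.5: allow a test at any time, and require dosing to be withheld, if pregnancy is suspected. An early pregnancy without signs raises no suspicion.
- Section 5.5: otherwise names only the screening test.

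None of these schedules a second test before dosing.

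**Step 5: how often.** The documents give no count of WOCBP, no pregnancy rate and no test sensitivity. Assume 30% to 40% of the 320 subjects are WOCBP and 0.2% to 0.5% of them have a pregnancy missed at screening.
- Low: 0.30 × 320 = 96 women; 96 × 0.002 = 0.19.
- High: 0.40 × 320 = 128 women; 128 × 0.005 = 0.64.
- With 1:1 allocation, half are on brexpiprazole: about 0.1 to 0.3.

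**Step 6: moving the Day 4 test versus keeping it.** For illustration, assume an equal chance on each day that a pregnancy becomes detectable, a 14-day-old screening test, and no detection on suspicion. Count days at risk × doses taken before the next scheduled test.

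| Schedule | Days on which a pregnancy becoming detectable is found after dosing | Doses before the test | Product |
|---|---|---|---|
| Current (Day 4, Day 21) | 14 + 3 = 17 | 3 | 51 |
| Test moved to Day 1 | 3 | 20 | 60 |
| Day 1 and Day 4 both | 3 | 3 | 9 |

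With a 7-day-old screening test, the current schedule gives (7 + 3) × 3 = 30, against 60 for the move. Moving the test cuts the number of exposed pregnancies (17 to 3 on this scale), but each remaining one is found later. Keeping both tests improves on both counts.

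**The case against.** The strongest reply is that the plan is consistent and already has safeguards. Table and text agree, Section 3.7.3.2 is satisfied by the screening test, and Exclusion 2 turns on a positive result, not on how recent a negative one is. A reader might infer a contradiction between the criterion and the schedule; there is none. This is a design choice that can be improved.

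A reader might also infer that any early pregnancy will come to light only after exposure. The documents do not support that. The screening test catches one already detectable, and Section 5.5 withholds dosing on suspicion. Subjects are inpatients from consent (Section 3.1), with only same-day passes authorized by the medical monitor (footnote a). Exclusion 1 requires two contraceptive methods or abstinence during the trial. Conception during screening is therefore unlikely. Fourteen days is the limit, and nothing says it is typical.

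All of that stands, and it narrows the point. It does not reach conception shortly before consent. Exclusion 1 looks forward from trial entry, Exclusion 4 admits subjects up to 4 weeks into the current manic episode, and the YMRS itself rates increased sexual interest and risky sexual behavior as part of the illness.

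**Conclusion.** The point holds as a low-frequency safety and eligibility-verification gap with a cheap remedy. The calendar facts (1 to 14 days, then 2 to 4 doses) come straight from the protocol. The group affected is women whose pregnancy is too early to detect at screening and raises no suspicion before Day 1.

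The expected number, about 0.2 to 0.6 randomized subjects, rests wholly on the assumed WOCBP share and missed-pregnancy rate. It should not be read as that many exposures to brexpiprazole, since about half would be on placebo.

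Nor should it be read as a threat to the primary analysis. Fewer than one subject in 320 would be withdrawn, the YMRS is rated at the Day 4 visit, and the effect on power and the treatment estimate is negligible.

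**What to change.** In Section 3.7.1.2 and the baseline column of Table 3.7-1, schedule a urine pregnancy test for WOCBP on Day 1, with a negative result required before the IWRS randomization call. Amend footnote a so that the baseline eligibility review includes this result.

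There are two ways to do it:
- **Move the Day 4 test to Day 1.** The number of tests is unchanged. The price is that a pregnancy becoming detectable between Day 1 and Day 4 has no scheduled test until Day 21, so this option is not free.
- **Add Day 1 and keep Day 4.** This removes that downside for one extra urine test per woman.

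Either way, the cost is an amendment to a table row, a footnote and one or two visit lists. In the same edit, state one test type consistently across the synopsis, Section 3.7.1.1 and Section 5.5.
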